The Benefit of Mindfulness-Based Intervention Using A Wearable Wellness Brain Sensing Device in the Treatment of Post Covid Symptoms

NCT05199233

07 Nov 2024

Mayo Clinic - NCT05199233

General Study Information

Principal Investigator: [name]

Co-principal investigators: [name] MD

Study Title: The Benefit of Mindfulness-Based Intervention Using A Wearable Wellness Brain Sensing

Device (Muse-STM) in the Treatment of Post Covid Symptoms

As of 07 Nov 2024

Research Ouestion and Aims

Hypothesis:

Post acute sequelae of SARS-CoV-2 infection (PASC), also known as "long haul covid" or Post-COVID Syndrome, is a significant cause of morbidity and disability in patients who have had COVID-19 with an estimated 10-30% of patients developing PASC with symptoms lingering for months and even years. These symptoms occur in a typical pattern, often including fatigue with post-exertional malaise, dyspnea, widespread pain, subjective cognitive dysfunction (often referred to as "brain fog"), and orthostatic intolerance and remain persistent. These can manifest in the post-covid patient as difficulty breathing or shortness of breath, tiredness or fatigue, difficulty thinking or concentrating, cough, chest and/or stomach pain, headache, palpitations, joint and/or muscle pain, parasthesias, diarrhea, increased anxiety and stress, as well as sleep problems.

We postulate that using a novel biofeedback-assisted meditation device (Muse-STM) daily can enhance calm state brain activity and parasympathetic nervous system activity in post-covid patients. We hypothesize that greater amount of time the patient uses this tool will directly correlate with improvements in stress, resilience, and overall quality of life.

Aims, purpose, or objectives:

In this study 60 patients diagnosed with Post-Covid Syndrome (PASC) at Mayo Clinic Rochester will be enrolled in this study.

Primary:

- 1. To study the feasibility of using a wearable brain-sensing wellness device (Muse-STM) to potentially reduce stress and anxiety during Post-Covid, which is characterized with increased stress and anxiety.
- 2. To assess the association between usage of the wearable brain-sensing wellness device (Muse-STM), and quality of life (QOL), subjective stress, anxiety, cognition, through self-assessment surveys.

Exploratory:

1. To collect data at month 6 (3 months post end of treatment) on continued use of Muse-STM past the treatment phase, as a proxy for lifestyle changes.

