All study participants will receive the Muse S^{TM} Headband system at study entry and will be asked to utilize it at least 4 times per week for a minimum of 10 minutes each time over a period of 3 months (12 weeks). They will be followed for a period of 6 months (3 months of treatment and 3 months post treatment) according to the schedule below.

We arable for LC

Pls: [name]; [name], PhD

Mayo Clinic - NCT05199233

	Consent /screen /baseline	Treatment Phase				Follow up Phase
Visit No.	1	2	3	4	5	6
Visit Type	Face to Face	Phone	Phone/ Email	Phone/ Email	Face to Face/ Phone/ Email	Face to Face/ Phone/ Email
Visit Days	0	2	30	60	90	180
Consent/Screening/						
Enrollment						
Informed Consent	X					
Inclusion/Exclusion	X					
Demographic and History	X					
Form	Λ					
Safety Data						
Depression	X		X	X	X	X
Adverse Events ¹			X	X	X	X
Concomitant Medication ²	X		X	X	X	X
Intervention						
Instructions for Muse-S TM & Fitbit [®] Tracker	X					
Muse-S TM use	X		X	X	X	
Fitbit [®] Tracker		X			X	X
Outcome						
CBS Cognitive Tests	X				X	X
Anxiety	X		X	X	X	X
Cognition Function	X		X	X	X	X
Emotional Distress	X		X	X	X	X
Quality of Life	X		X	X	X	X
Resilience	X		X	X	X	X
Self-Efficacy	X		X	X	X	X
Sleep	X		X	X	X	X
Stress Scale	X		X	X	X	X
Satisfaction Survey						X
End of Study Forms						X

^{1 =} For visit 5 & 6 only serious adverse events will be newly collected; 2 = For visit 5 & 6, only newly added concomitant medications will be collected

Study Visit Windows:

Each visit will have a window from the midpoint of the prior visit to the midpoint of the latter visit.

Data Collection:

Mayo Clinic - NCT05199233

Subjects will have the options of completing study surveys/questionnaires online via email link to REDCap prior to study visit. If not completed by the time the study visit takes place, the coordinator can provide the iPad digital version of the survey/questionnaire to the subject for the in-person visits or can interview the patient via phone for the telephone visits. If a subject misses a visit, the study staff will connect with the subject to collect what study data is appropriate through a simple virtual connection (email redcap surveys or telephone interview of surveys). Data Collection in this study will utilize REDCap⁴. All other data collection will be entered directly into a password protected system.

Assessments:

Safety:

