Use of Muse-STM Headband systems will be demonstrated to each participant prior to their first mindfulness practice session, which will be completed during the baseline visit with the study coordinator. The study coordinator will present the participant with detailed instructions on how to begin each session. The frequency of the sessions thereafter will be at the participant's discretion according to the study's requirements (daily practice). Mindfulness training will follow the protocol in the Muse-STM

APP, which follows a standard breathing exercise with EEG brain state feedback through the mobile device, as designed by a panel of experienced mindfulness practitioners. In short, the Muse- S^{TM} functions like a $FitBit^{\textcircled{R}}$ like device for the brain.

The study participants can access 3 different types of meditation while using the Muse-STM Headband system. They are as follows:

Wearable for LC PIs: [name]; [name], PhD Mayo Clinic - NCT05199233

• Mind Meditation uses the Muse-STM headband to track the user's brain activity during meditation and translates the brain's activity into guiding sounds. This is a classic focused attention on the breath meditation, where you get real time feedback on your brain. Users get real time feedback to know when they are in focused attention and when their mind is wandering and are cued to return to a state of focused attention (meditation state). Users also see data from their brain after the meditation. Real time feedback during Mind Meditation is the Muse-STM signature meditation and teaches the fundamentals of a meditation practice in remaining in a calm focused attention state and being able to move your mind away from distracting thoughts. This teaches them the skill to notice their minds and learn to direct themselves out of their discursive mind and onto a neutral object like their breath, while giving them neurofeedback to guide them when they are "doing it right" and reinforce the learning. It is recommended that Muse Mind be done daily for a minimum of 5 minutes per day. Users can do more if they choose.

- **Guided Meditation** These are different breathing exercises where different breathing techniques, such as box breathing, 6-4 breathing, etc., are taught to help the individual regulate their breath. The participant is given real time feedback to keep them breathing along in time with the guide.

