Please note: Patients must have access to an iOS or Android capable device to take part in this study in order to interact with the Muse-STM Headband system.

Treatment phase:

During the first three months of study, participants will be asked to complete the online study intervention using the Muse-STM headband. Participants will be contacted via telephone and online (REDCap) for study visits at day 2, 30 and 60. At day 90, they will be asked to return to the clinic for an in-person visit (telephone and online will be alternatives).

Study Follow-Up Visits:

The study will consist of a 6-month visit post baseline (3-month post end of intervention). Participants will be asked to complete an in-person visit, if possible (telephone and online will be the alternative), which will include a second POCUS exam.

Subject Information

Target accrual: We plan to recruit 80 patients diagnosed with Post-Covid Syndrome at Mayo Clinic with the intent of enrolling 60 to study.

Subject population: A total of 60 patients diagnosed with Post-Covid Syndrome at Mayo Clinic who meet the following study criteria:

Inclusion Criteria:

- 1. 18 years of age or older at time of consent
- 2. Identified with Post-Covid Syndrome (PASC) at Mayo Clinic Rochester:

Wearable for LC

PIs: [name]; [name], PhD

Mayo Clinic - NCT05199233

- 3. Not pregnant by subject self-report at time of consent
- 4. Have the ability to provide informed consent
- 5. Have the ability to complete all aspects of this trial
- 6. Have access to an iPhone, iPad, or Android device
- 7. Have no contraindicating comorbid health condition which would interfere with the proper use of the Muse-STM system, as determined by the clinical investigators

Exclusion Criteria:

- 1. Used an investigational drug within the past 30 days
- 2. Anyone that is not on a stable dose of medication for anxiety, depression or sleep
- 3. Currently (within the past 3 weeks) been practicing mindfulness training on a weekly/regular basis
- 4. Currently (within 3 weeks) has been enrolled in another clinical or research program which intervenes on the patients' QOL, or stress
- 5. An unstable medical or mental health condition as determined by the physician investigator

Data Analysis

Data Analysis Plan:

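### Adverse events are first asked about at visit 3 (nominal day 30), although device use starts on day 0 and a day 2 call to every participant is already planned

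*Combined protocol and SAP*

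**What the plan says.** **Start of exposure.** Under Intervention, the Muse-S Headband system is demonstrated before the participant's "first mindfulness practice session, which will be completed during the baseline visit with the study coordinator". The baseline visit is visit 1, day 0.

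**Contacts.** Under Treatment phase: "Participants will be contacted via telephone and online (REDCap) for study visits at day 2, 30 and 60". The schedule lists visit 2 as a phone visit and visit 3 as phone or email.

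**Adverse event collection.** In the Safety Data block of the schedule, the row "Adverse Events" is empty at visits 1 and 2 and marked at visits 3, 4, 5 and 6. Its footnote reads: "For visit 5 & 6 only serious adverse events will be newly collected". The only item marked at visit 2 is the Fitbit tracker.

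**Windows.** Under Study Visit Windows: "Each visit will have a window from the midpoint of the prior visit to the midpoint of the latter visit".

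**General follow-up.** Under Data Collection: "If a subject misses a visit, the study staff will connect with the subject to collect what study data is appropriate". Under Adherence to Intervention, staff review the application reports and contact participants whose data are not arriving. Neither provision mentions adverse events, and the second sets no time.

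**Overlap with the disease.** The Hypothesis section lists post-COVID symptoms that include "headache, palpitations, joint and/or muscle pain, parasthesias, diarrhea, increased anxiety and stress, as well as sleep problems".

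**The concern.** Staff following the schedule supervise the first session on day 0 and telephone every participant shortly afterwards, but have no adverse event item to complete at either contact. The first enquiry comes weeks later, possibly by email, and must cover everything since day 0. Non-serious events get one further enquiry, at visit 4.

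This is a feasibility study whose primary hypothesis is that patients will find the headband easy to use and will use it as the protocol asks. If some participants stop in the first weeks, the reader will want to know whether discomfort or something else was the cause. The satisfaction survey cannot answer that, because it is marked only at visit 6.

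There is also a classification problem. Headache, palpitations and paraesthesias are part of the condition under study, and no scored baseline scale is described as measuring them. Such a complaint, recalled a month later, is hard to class as new, worse or pre-existing.

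**Working it through.** The plan states no adverse event rate, drop-out rate or related calculation, so there is no figure of its own to reproduce. The check covers the table reading and then the timing.

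**Is the table read correctly?** The table text is broken, so the columns were tested against other statements.
- The Fitbit row, read the same way, gives visits 2, 5 and 6. The Fitbit Tracker section names the same three visits.
- The Depression row gives visits 1, 3, 4, 5 and 6, which leaves visit 2 empty.
- The footnote on visits 5 and 6 fits an adverse event row that ends with marks at those visits.

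The reading of visits 3 to 6 is therefore sound.

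**Windows.** Inputs: scheduled days 0, 2, 30, 60, 90 and 180, and the midpoint rule. The window for a visit runs from (previous day + own day)/2 to (own day + next day)/2.

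| Visit | Nominal day | Window | New events solicited |
|---|---|---|---|
| 2 | 2 | (0+2)/2 = 1 to (2+30)/2 = 16 | none |
| 3 | 30 | 16 to (30+60)/2 = 45 | all |
| 4 | 60 | 45 to (60+90)/2 = 75 | all |
| 5 | 90 | 75 to (90+180)/2 = 135 | serious only |

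**Recall.** An event at the first session is first asked about after 16 to 45 days, nominally 30. That is 16/7 = 2.3 to 45/7 = 6.4 weeks. As a share of the 84-day (12-week) treatment period, day 30 is 30/84 = 36% and day 45 is 45/84 = 54%.

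**Sessions before the first enquiry.** The Methods section asks for at least 4 sessions per week; the Intervention section refers to daily practice. The two statements need to be reconciled, so both are shown.

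| First enquiry on day | At 4 per week (4 × day/7) | Daily |
|---|---|---|
| 16 | 9.1 | 16 |
| 30 | 17.1 | 30 |
| 45 | 25.7 | 45 |

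**Gain from using visit 2.** On nominal days, 30 − 2 = 28 days. The same window rule applies to visit 2, however, and its latest day (16) equals the earliest day of visit 3. The gain can therefore shrink to nothing at the edges.

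**Participants at risk of leaving unasked.** The documents give no early drop-out rate. Assuming 5% to 20% stop before visit 3, 60 × 0.05 = 3 to 60 × 0.20 = 12 of the 60 would leave without a scheduled adverse event question. This is an upper bound for each rate, because it supposes that the general follow-up contacts recover nobody.

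**A related gap.** The last enquiry about new non-serious events is visit 4, nominally day 60 and at latest day 75. Treatment runs to day 84, so the last 84 − 60 = 24 days (or 84 − 75 = 9 days) are not covered either.

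**The case against.** The strongest reply is that the consequence is modest and easily exaggerated. Much of it stands.

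- **Early stoppers are not necessarily missed.** A reader might infer that anyone who stops before visit 3 is never asked about adverse events. The documents do not support that. Staff contact people whose device data are not arriving, and try to reach those who miss a visit. These contacts could bring out an event, but neither names adverse events, so they narrow the gap without closing it. Nothing bars staff from recording an event volunteered on the day 2 call. Consent pages were removed from the supplied text, so any reporting instructions there cannot be judged.
- **No planned estimate is biased.** A reader might infer that the feasibility result will look too favourable. The primary outcome is frequency and duration of use, taken from session data in the cloud and summarised descriptively. Early abandonment shows there whether or not an event is recorded. The Data Analysis Plan contains no adverse event rate or tolerability endpoint.
- **Baseline is not empty.** Anxiety, emotional distress, sleep, depression and cognitive function are scored at visit 1, and the post-COVID phenotype is recorded. The baseline point is left with the physical symptoms.
- **No event profile is given.** It is tempting to call headache or palpitations the likely effects of the headband, or to treat intolerance as the main reason for giving it up. The documents say neither. They list these only as symptoms of the disease.

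What remains is the schedule itself: two early contacts with every participant, and no adverse event item at either.

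**Conclusion.** The point holds as a cheap improvement to the schedule. Adverse events are first solicited at nominal day 30 (day 16 to 45), after about 17 sessions at 4 per week, although first use is on day 0 and a call is already planned for day 2. New non-serious events are solicited at two visits only. The cost is a less complete safety record for the first weeks and less knowledge of why early users stop. The adherence summary is unaffected.

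The timing follows directly from the schedule and the window rule. The count of 3 to 12 participants rests on an assumed drop-out rate and shows scale only; the conclusion does not depend on it. That events are actually forgotten or lost is a reasonable inference, not something the documents show.

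**What to change.** - In the schedule, mark Adverse Events at visit 1, to be completed after the supervised session, and at the existing visit 2 call.
- Optionally, before that session, note the presence and severity of the physical post-COVID symptoms in the Hypothesis section that no scored scale covers, such as headache, palpitations and paraesthesias. Later events can then be classed as new or worsened.

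The visit 2 enquiry is early only if the call is held near day 2. By then a participant at 4 sessions per week has had about 4 × 2/7 = 1.1 sessions' worth of the requested use besides the supervised one. The change therefore catches reactions to first use; events that arise after the call still wait for visit 3.

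Cost: two schedule marks and, if wanted, a short checklist. That means a few minutes on contacts already planned and a few more minor events to record.

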Wearable for LC PIs: [name]; [name], PhD Mayo Clinic - NCT05199233

The primary outcome will be the adherence to the Muse-STM by summarizing the frequency of use and duration of use each time it was accessed.

The secondary outcomes will include:

o change in quality of life (QOL), stress, anxiety, and cognition, score over time

Background:

According to the CDC, new or ongoing symptoms of long COVID may include difficulty breathing or shortness of breath, tiredness or fatigue, difficulty thinking or concentrating, cough, chest and/or stomach pain, headache, heart palpitations, joint and/or muscle pain, pins and needles, diarrhea, sleep problems; all of which can increase anxiety and stress in the post-covid patient.

Integrative Medicine has introduced many mind-body therapies for addressing mental stress. The top stress relievers recommended by Mayo Clinic include: getting active, eating a healthy diet, avoiding unhealthy habits, meditation, laughing more, connecting with others, asserting yourself, practicing yoga, getting enough sleep, keeping a journal, exploring music and being creative, seeking counseling². Among all of these potential options, meditation is the easiest to incorporate in a current lifestyle yet most difficult to undertake without proper training and guidance at the beginning. Muse-STM is a clinical grade, headband-style wireless EEG system designed to interact with a mobile device (a smartphone or tablet) (https://choosemuse.com). In combination with the Muse-STM APP running on iOS or Android smartphones, Muse-STM converts EEG signals measured over the frontal and temporal cerebral cortices into measures of brain state. At the same time Muse-STM can also guide the user through the meditation steps. Calibrated to an individual user, Muse-STM distinguishes between active and calm brain states to provide real-time performance feedback, and helps users realize the benefits of mindfulness practice in an engaging and accessible manner. Muse-STM also has a PPG sensor that tracks heartrate during meditation sessions as well. This has been tested in a prior study by some of the current study team (SP and ITC), with patients undergoing breast cancer surgery³ and is currently being test in patients with fibromyalgia who concurrently experience pain (ITC and RG) and in healthcare providers who are under stress (ITC).

Study Design and Methods

Methods:

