• Depression: The PHQ-2^{5,6} is a validated and frequently used self-report measure of depressive symptoms comprising of 2 questions, which were derived from the PHQ-9^{7,8}.

Outcomes:

- Demographics Form: This form collected demographic and other lifestyle history of the research subject.
- Quality of Life: Will be measured using the *Linear Analogue Self-Assessment (LASA)*⁹⁻¹¹. This is a six-item measure of quality of life (QOL), in which QOL is conceptualized as a multidimensional construct with five domains (physical, functional, emotional, spiritual, and social). This data will be collected at screen (prior to any treatment), day 30, day 60, day 90 end of treatment, and day 180 end of study (3 months post last treatment).
- Anxiety: State-Trait Anxiety Inventory (STAI-Y1)¹²⁻¹⁶ This 20-item self-report measure indicates the intensity of feelings of anxiety; it distinguishes between state anxiety (a temporary condition experienced in specific situations) and trait anxiety (a general tendency to perceive situations as threatening). It uses a 4-point visual analog scale, and the participant indicates how they feel in the moment (1 = not at all to 4 = very much so).
- Stress: Will be evaluated through the *Perceived Stress Scale (PSS)*^{17,18}. The PSS is a 10-item Likert scale that measures global life stress by assessing the degree to which experiences are appraised as uncontrollable or unpredictable. Scores can range from 0 to 40, with higher scores indicating greater perceived stress. Reliability is reported as 0.85, with Cronbach alphas ranging from 0.75-0.86.
- Resilience: Will be evaluated through the *Connor-Davison Resilience Scale 10 (CD-RS10)*¹⁹. This is a 10-item, Likert scale, validated scoring system. The CD-RS10 is a reliable means of assessing resilience and is most often used in medical and/or disaster studies²⁰.

Sleep Quality:

(ASCQ-Me® v2.0 Sleep Impact - Short Form²¹) is an effective instrument used to measure the impact sleep has on overall health in adults. The ASCQ-Me Sleep Impact SF is equivalent to the PROMIS Sleep Disturbance and Sleep-Related Impairment Surveys except the scoring is reversed.²¹ The PROMIS surveys indicate greater symptom burden as the score goes higher and the ASCQ-ME survey indicates better health as the score goes up. The Sleep Impact Scale consists of 5-item, likert scale, validated, scoring system.²² The 5 questions focus on experiences in the prior 7 days.

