Participants will be asked to wear their Fitbit® 24/7 except during a time of recharging. Fitbit® Data will be collected at visits 2, 5 and 6 by the study team and from participants Fitbit® app that has been downloaded on their personal electronic device. The data collected will include Heart Rate, steps, sleep quality, and blood oxygen saturation level (SpO₂).²⁹ A Fitbit® account will be created by each study participant with the help of the research coordinator to allow us to track study participation. Information collected from the Fitbit® app will be logged into the database. This approach for working with the Fitbit has been successfully used in the past by Mayo investigators.³⁰

Subject Retention:

Participants will not be remunerated for participating in this study, but they will be allowed to keep the Muse-STM Headbands and Fitbit[®].

Study Design:

We will use standardized procedures to ensure uniform instructions and support for all subjects for the recruitment, screening, and study entry.

Recruitment:

Mayo Clinic - NCT05199233

Patients with Post-Covid Syndrome will be recruited from the Mayo Clinic Practice. The study staff will inform participants of the study during practice meetings, and if the participants indicate interest, they will connect with research staff and arrange a time to meet to begin the consent process.

Participants will not be reimbursed for their time spent in the study, but all participants will be given the option of keeping the Muse-STM Headband system as well as the Fitbit[®] tracker for continued use post study participation.

Consent and Screen:

Study coordinator will meet with the potential participant who has expressed an interest in participating in the study. The study coordinator will begin by introducing the study details, and after determining that the subject has continued interest in study participation, will move on to the study consent. If the subject chooses to consent, the study coordinator will screen the participant for study entry inclusion/exclusion criteria.

Once a subject meets all entry criteria, the post-covid phenotype, as designated by the Post-Covid Clinic staff, will be recorded and the subject will begin study participation. At this point, they will be asked to complete the study surveys/questionnaires. Finally, a POCUS will be performed during this first face to face visit if one has not been completed clinically in the previous 2 weeks.

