Demographic characteristics are described using mean and standard deviations or frequencies and percentages based on the type of variable. For the primary aim of assessing feasibility, descriptive statistics and graphical displays will be presented for data obtained on frequency and duration of use over the 12 weeks of treatment. A linear mixed model with repeated measures for each time point that stress and sleep were taken will be utilized to estimate the association between the number of sessions spent using the Muse-STM with the stress and sleep level outcome. As secondary outcomes, the results of the LASA, resilience, coping, and cognitive testing will be analyzed using similar mixed models. In all cases, results will be summarized using point estimates and corresponding 95% confidence intervals. Given the number of outcomes assessed, all analyses will be considered exploratory.

Endpoints:

Primary Hypothesis:

a) Post Covid patients enrolled in this study will find the Muse-STM Headband system easy to use and will use it per protocol.

Secondary Hypotheses:

- a) Stress score will be lower and sleep score will be improved when compared to the baseline measures for those who use the Muse-STM system as directed.
- b) As the use of the Muse-STM system increases, QOL, resilience and coping will improve.

References

1. Ninifaggi F. Physician engagement: mindfulness as part of the pandemic solution. Elsevier Connect. https://www.elsevier.com/connect/physician-engagement-mindfulness-as-part-of-the-pandemic-solution. Updated 11 May 2020. Accessed 11 June 2020, 2020.

- 2. Mayo Clinic Staff. Stress Management. Healthy Lifestyle Web site.

 https://www.mayoclinic.org/healthy-lifestyle/stress-management/in-depth/stress-relievers/art-20047257. Updated 12 March 2019. Accessed 01 June 2020.

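### Secondary hypothesis (a) sets one arm against a single baseline while illness duration and visit time go unmodelled, so natural recovery could be misread as device benefit

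*Combined protocol and SAP*

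**What the plan says.** - **Entry.** Subject Information, inclusion criterion 2, requires patients "Identified with Post-Covid Syndrome (PASC) at Mayo Clinic Rochester". No inclusion or exclusion criterion mentions time since infection or symptom onset. The Hypothesis section describes "symptoms lingering for months and even years", so short and long illness can both enter.
- **Baseline data.** Of the demographics form, the Assessments section says: "This form collected demographic and other lifestyle history of the research subject". Under Consent and Screen, "the post-covid phenotype, as designated by the Post-Covid Clinic staff, will be recorded". No schedule row or described form names an infection date, onset date or symptom duration.
- **Design.** One arm: "All study participants will receive the Muse" headband at entry (Methods). The questionnaires have one pre-treatment measurement, at visit 1.
- **Outcomes.** The primary outcome is adherence. The secondary outcomes are "change in quality of life (QOL), stress, anxiety, and cognition, score over time". Secondary hypothesis (a), under Endpoints, reads "Stress score will be lower and sleep score will be improved when compared to the baseline measures", restricted to those who use the system as directed. The title begins "The Benefit of Mindfulness-Based Intervention Using A Wearable Wellness Brain Sensing".
- **Model.** The Data Analysis Plan relates the number of sessions to stress and sleep in a linear mixed model with repeated measures. It names no fixed effect for visit and no term for time since infection. It does not say whether sessions are counted cumulatively or per interval. Results are point estimates with 95% intervals, and all analyses are labelled exploratory because of the number of outcomes.

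**The concern.** Patients who are still recovering and patients on a plateau can be mixed, and nothing planned tells them apart. With one arm and one baseline, any improvement that would have happened anyway enters the change from baseline in full. Hypothesis (a) would then appear supported with no device effect at all.

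The usage model does not escape the problem. Cumulative sessions rise with calendar time, and so does natural recovery. Without a visit term the model can credit recovery to sessions. Even with a visit term, confounding remains if recently infected patients both recover faster and use the device more or less than others. This bears on primary aim 2, which is the association between usage and quality of life, stress, anxiety and cognition.

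**Working it through.** The plan has no figure to reproduce: it gives 60 patients, with no power, SD, correlation or expected change. What follows is illustration under stated assumptions.

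**1. Change from baseline, no device effect**

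Inputs: n = 60 (document); correlation r between baseline and day 90 of 0.6 or 0.7 (assumed); natural improvement d of 0.2 or 0.3 SD (assumed). The plan does not say how hypothesis (a) will be judged; I take it to be the 95% interval for mean change.

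SE in SD units = sqrt(2(1 − r)/n)
- r = 0.6: sqrt(0.8/60) = 0.115; half-width 1.96 × 0.115 = 0.23 SD
- r = 0.7: sqrt(0.6/60) = 0.100; half-width 0.20 SD

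P(interval excludes zero) = 1 − Φ(1.96 − d/SE)

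| r | d = 0.2 SD | d = 0.3 SD |
|---|---|---|
| 0.6 | 41% | 74% |
| 0.7 | 52% | 85% |

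Hypothesis (a) covers only as-directed users, and their number is unknown. If 36 of the 60 qualify (assumed), then at r = 0.6 the SE is sqrt(0.8/36) = 0.149 and the two probabilities fall to 27% and 52%.

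**2. The same on the Perceived Stress Scale (range 0 to 40)**

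With n = 60, SD 6 to 8 and r 0.5 to 0.7 (all but n assumed), the half-width is 1.2 to 2.0 points. The interval excludes zero in 16–38% of trials for a natural improvement of 1 point, 49–92% for 2 points and 83–100% for 3 points.

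**3. The session model, no device effect**

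Simulation with a random-intercept model: days 0, 30, 60 and 90, n = 60, SD 7, r = 0.6, cumulative sessions over 12 weeks averaging 4 a week and varying between people, and recovery unrelated to use. There were 400 runs per setting, so the Monte Carlo SE at 5% is sqrt(0.05 × 0.95/400) = 1.1 percentage points.

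| Natural improvement by day 90 | False session association, no visit term | With visit term |
|---|---|---|
| 0 points | 4% | 5% |
| 1 point | 25% | 4% |
| 2 points | 60% | 6% |
| 3 points | 93% | 7% |

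A visit term brings the rate back to about 5%. It does so here because recovery speed was simulated as independent of use. Where the two are linked through illness duration, time since infection is also needed.

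**4. Regression to the mean**

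Expected regression = (1 − r) × the amount by which the enrolled group's mean lies above the level it regresses to. With no score-related selection this is zero. With a 0.25 SD shift at r = 0.6 it is 0.4 × 0.25 = 0.10 SD, and the interval would exclude zero in the beneficial direction in about 14% of trials.

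**The case against.** The primary outcome is adherence, which natural recovery does not directly inflate. The planned model speaks of association, and every analysis is labelled exploratory. A reader might infer from the title that improvement *will* be presented as device benefit. The document does not support that; it supports only that it *could* be. The exploratory label does not fully answer the point, however, because the reason given for it is multiplicity, and no caution about uncontrolled change appears.

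A reader might also infer that infection date is not collected. That goes too far: the history form is not reproduced, and criterion 2 ends in a colon at a page break, so a sub-list may have been lost. What can be said is that no section states that it is recorded. Likewise, the mention of repeated measures at each time point might be taken to imply a visit effect, but none is named.

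A third tempting step is that the open time window produces regression to the mean. It does not. Regression to the mean comes from selection at a bad score, and no criterion uses a stress, anxiety, sleep or quality-of-life threshold. Stable medication is required and unstable conditions are excluded, although neither criterion limits gradual recovery.

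Two further objections stand. Without a comparator, adjusting for illness duration cannot isolate a device effect on change from baseline. A median split by duration would also be too imprecise: with 30 per half, the half-width for the difference in change is 1.96 × sqrt(2 × 0.8/30) = 0.45 SD at r = 0.6, and 0.39 SD at r = 0.7, both wider than the 0.2 to 0.3 SD at issue.

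**Conclusion.** The point holds for secondary hypothesis (a) and for the usage models. It does not touch the adherence outcome. As written, the plan could count natural recovery as support for the device.

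The 41–85% range depends on the assumed 0.2 to 0.3 SD recovery, on r of 0.6 to 0.7 and on all 60 patients contributing; fewer as-directed users lower it. The false usage association shown by simulation depends on cumulative counting and the absence of a visit term. The route through differential use by recently ill patients is possible but not shown. Regression to the mean would add to the bias only if patients enrol when worse than usual, which the document does not show. A limit on time since infection would not by itself cure a single-arm comparison. This is a cheap improvement to a feasibility study and leaves its design intact.

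**What to change.** 1. Record the date of the qualifying COVID-19 infection on the visit 1 history form, with a chart look-up for anyone already enrolled.
2. In the mixed models, alongside sessions, include visit as a main effect, time since infection, and the interaction of time since infection with visit. State whether sessions are cumulative or per interval.
3. Show change by illness duration descriptively only, without a subgroup test.
4. State in hypothesis (a) and in the conclusion that change from baseline is uncontrolled change during use and is not evidence of device benefit.

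The cost is one form field, a few degrees of freedom, slightly wider intervals and a less favourable conclusion. These steps reduce confounding and correct the claim. They do not identify a device effect on change from baseline, which would need a concurrent comparator or a run-in with repeated baselines.
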